8. STATISTICAL METHODS AND ANALYSIS

8.1 General Statistical Conventions

All statistical procedures will be completed using SAS 9.4® or higher.

Unless otherwise stated, all statistical testing will be two-sided and will be performed using a significance (alpha) level of 0.05, and two-sided 95% confidence intervals (CI) will be provided when relevant.

Continuous variables will be summarized using descriptive statistics, including number of subjects (n), mean, median, standard deviation (SD), minimum and maximum. For efficacy variables with subscales, the total score and subscales will be summarized.

For categorical variables, summaries will include counts of subjects and percentages. Percentages will be rounded to one decimal place.

Unless otherwise stated all summaries will be presented by treatment group.

All subject data, including those derived, will be presented in individual subject data listings. Unless otherwise stated, unscheduled visit results will be included in date/time chronological order, within subject listings only. All listings will be sorted by treatment group, subject ID, date/time and visit/study day. Subject's sex and age will be stated on each listing. Unless otherwise stated, data listings will be based on All Subjects Randomized Set.

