8.5.1.2 Mixed model repeated measures analysis

A mixed model repeated measures analysis using ‘direct likelihood’ will be performed for continuous efficacy outcomes. The SAS procedure PROC MIXED will be used. The preferred model will include the fixed effects of treatment, visit, treatment-by-visit interaction, and the baseline value of the endpoint variable as a covariate. An unstructured matrix for the variance-covariance will be used. The denominator degrees of freedom will be calculated according to the Kenward-Roger method.

In case of non-convergence of the preferred model or memory issues, the following back-up models are defined:

1. The same as the preferred model, but the Kenward-Roger method will be replaced by Satterthwaite approximation.

2. The same as the preferred model, but with handling of the selection of the covariance structure for the final model in a hierarchical fashion, with the order being Toeplitz, AR (1), and compound symmetry, respectively.

The second back-up model will only be used if the first back-up model does not converge or has memory issues.

The model will provide least-squares mean estimates, standard errors, two-sided 95% confidence intervals and p-values (where applicable) for mean change at all visits between treatments (NAL ER vs. placebo).

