8.6. Multiplicity

In order to control for Type, I error (0.05), a fixed sequence testing procedure will be used on the primary and 3 key secondary endpoints. All endpoints will be tested (NAL ER treatment arm versus the placebo arm) at the 0.05 level of significance, following a pre-specified order. As soon as one endpoint assessment is found to be non-significant, subsequent endpoints will not be assessed. The rank order of testing is specified below.

- Time to onset of effect on pruritus as measured by proportion of participants with an improvement (reduction) in WI-NRS by ≥ 4 from baseline during the 14-week treatment period.
- Change in Investigator Global Assessment-Prurigo Nodularis (IGA-PN) as assessed by the percentage of subjects having a 1-category improvement in activity.
- The mean change in 7-day average WI-NRS from baseline to Week 14 for the NAL ER treatment arm versus the placebo arm.
- Change in PAS as assessed by the percentage of subjects having a 1-category improvement in the percentage of prurigenous lesions with excoriations/crusts (item 5a) from baseline to Week 14 for the NAL ER treatment arm versus the placebo arm.
- Change in PAS as assessed by the percentage of subjects having a 1-category improvement in the percentage of healed lesions (item 5b) from baseline to Week 14 for the NAL ER treatment arm versus the placebo arm.
- Change in PAS as assessed by the percentage of subjects having a 1-category improvement in the percentage number of lesions (item 2) from baseline to Week 14 for the NAL ER treatment arm versus the placebo arm.
- The mean change in ItchyQoL from baseline to Week 14 for the NAL ER treatment arm versus the placebo arm.

- The mean change in sleep disturbance (PROMIS Sleep Disturbance Short Form 8a) from baseline to Week 14 for the NAL ER treatment arm versus the placebo arm.
- The proportion of subjects having a PBI-P score of ≥ 1 at Week 14 for the NAL ER treatment arm versus the placebo arm.

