8.6 Analysis of Primary Efficacy Endpoint

Hypothesis:

The null hypothesis is that there is no treatment group difference (NAL ER vs. placebo) for the primary efficacy endpoint and the alternative hypothesis is that a treatment group difference exists.

Statistical Decision Rules

Unless otherwise indicated, all tests will be 2-sided, and differences resulting in a p-value <0.05 will be considered statistically significant.

The primary efficacy endpoint is the difference between the percent responders at Week 14 for the NAL ER treatment arm versus the placebo arm.

A responder is defined as a subject with a ≥ 4 -point decrease in the 7-day average WI-NRS from baseline to Week 14.

The proportions of responders in NAL ER and placebo will be compared using a logistic regression model, with baseline WI-NRS as a covariate and country as fixed effect, as described below. Missing Week 14 WI-NRS data will be set to missing.

Sample SAS code:

```
proc genmod data=winrsa descending; where avisitn ge 3;
class usubjid avisitn trt posite ;
model resp = trt avisitn avisitn*trt posite base
/ dist=binomial;
repeated subject=usubjid / withinsubject=avisitn
type=un;
lsmeans trt*avisitn /cl ilink diff oddsratio;
Ods output diff=diff lsmeans=lsm ;
run;
```

* Estimate Response rate and SE;

Recoding the resp to a new resp variable

```
data winrsa; set winrsa;
if resp = 0 then respnw = 2;
else if resp= 1 then respnw = 1;
run;
```

Using proc freq to create the binomial dataset;

```
proc sort data = winrsa; by avisitn trt;
proc freq data = winrsa; by avisitn trt;
tables respnw/ out = FreqCount binomial ;
exact binomial;
ods output binomial=bin;
run;
```

The variable *_bin_* is the response rate for resp = 1;
The variable for SE is *E_bin*

* Estimate Odds ratio and CI;

These are provided in the diff dataset and can be output directly.

run;

Sensitivity analysis

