8.6.2. Subgroup analyses

Additional subgroup summaries will be performed for the primary endpoint to determine whether differences exist in primary endpoint results between subgroups. These subgroup summaries will be carried out using the subjects from the mITT.

The list of potential subgroups (with applicable definitions in parentheses) includes, but is not necessarily limited to, the following:

- Age (18-39, 40-64, 65+ years)
- Sex (Female vs. Male)
- History of diseases associated with, or risk factors for, prurigo nodularis, as described in
 - Dermatologic diseases;
 - Conditions associated with metabolic itch (e.g., liver, renal or endocrine);
 - Atopy (including atopic dermatitis alone, if the numbers are large enough);
 - Neurologic conditions associated with itch;
 - Other.

These medical history subgroup analyses will be performed if the smaller of the 2 groups (with or without the condition) has at least 30 subjects. Additional post-hoc subgroup evaluations may be performed if the initial observations warrant it.

For each subgroup variable, the frequency and percentage of responders for each category will be displayed by treatment group. The difference in response rate between the treatment groups and 95% CI will also be presented. These subgroup analyses will be considered exploratory, as they do not control for multiplicity.

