8.6.3 Analysis of secondary efficacy endpoints

All secondary endpoints will be analyzed using the mITT population.

MMRM without imputation for missing data:

The following secondary efficacy endpoints will be analyzed using a mixed model for repeated measures (MMRM):

- The mean change in 7-day average WINRS from baseline to Week 14 for the NAL ER treatment arm versus the placebo arm;
- The mean change in ItchyQoL from baseline to Week 14 for the NAL ER treatment arm versus the placebo arm;
- The mean change in sleep disturbance (PROMIS Sleep Disturbance Short Form 8a) from baseline to Week 14 for the NAL ER treatment arm versus the placebo Arm.

The analysis of change from baseline to week 14 will be performed utilizing all observed data for visits up to and including Week 14, without imputation for missing data. The model used for this analysis will include the fixed effects of treatment, visit, treatment-by-visit interaction, and baseline value. An unstructured variance-covariance matrix will be used in the analyses. The comparison of interest is the treatment difference at Week 14. The model will provide least-squares mean estimates, standard errors, two-sided 95% confidence intervals and p-values for mean change at all time points between treatments (NAL ER vs. placebo) for ItchyQoL (total score and subscales: symptoms, functional limitations, emotions) and PROMIS. The same statistics will be provided for WI-NRS, except for the p-values.

Sample SAS code:

```
PROC MIXED data=xxxx;
  CLASS visit treatment subjid;
  MODEL CHG = treatment visit treatment*visit baseline/solution DDFM=KENWARDROGER;
  REPEATED visit / type=un subject=subjid;
  LSMEANS treatment*visit / pdiff CL;
  ODS output Diffs=outdata1 LSMeans=outdata2;
RUN;
```

Sensitivity analyses: MMRM with imputation for missing data

We will use the imputation methods described above for the primary efficacy endpoints to assess the sensitivity of missing data on inference regarding the secondary endpoints. Since these are continuous measures, we will use the delta methods described above.

Summary for Categorical Endpoints:

The count and percentage will be provided for the following endpoints:

- Change in PAS as assessed by the percentage of subjects having a 1-category improvement in the percentage of prurigenous lesions with excoriations/crusts (item 5a) from baseline to Week 14 for the NAL ER treatment arm versus the placebo arm;

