12 APPENDIX

12.3 Programming Guidance Document for Multiple Imputation, Control –based Imputation & Tipping Point Analysis

Introduction.

This appendix describes three approaches to multiple imputation.

1. Simple Multiple Imputation;
2. Control- based Imputation;
3. Tipping Point Analysis.

All of these are being implemented in data sets that have repeated measures data collected from subjects at multiple time points.

The primary efficacy endpoint is defined as the difference between the percentage of “Responders” at Week 14 for the NAL ER treatment arm versus the placebo arm. A “Responder” is defined as a subject with a ≥ 4 -point decrease in the 7-day average WI-NRS from baseline to Week 14.”

Secondary endpoints are:

- The mean change in ItchyQoL from baseline to Week 14 for the NAL ER treatment arm versus the placebo arm;
- Change in PAS as assessed by the percentage of subjects having a 1-category improvement in the percentage of prurigenous lesions with excoriations/crusts (item 5a) from baseline to Week 14 for the NAL ER treatment arm versus the placebo arm;
- The mean change in sleep disturbance (PROMIS Sleep Disturbance Short Form 8a) from baseline to Week 14 for the NAL ER treatment arm versus the placebo arm.

Multiple imputation is a missing data approach that assumes that the missing data is missing at random (MAR), i.e., that the probability of missing is not a function of the values that are missing but only depend on the observed responses.

The advantage of MI over single imputation is that it allows one to adjust the variance to account for the imputation of the missing data.

All of the data sets on which imputation is applied are longitudinal data sets, specifically the following ADaM datasets: ADEFF and ADQS. Please note: ADEFF will use 4 visits (AVISITN 2-5/ Week 2, 6, 10, 14)

ADQS will use 3 visits (AVISITN 3-5/Week 6, 10, 14).

The following is an explanation of the process.

This is a guidance document. It does not provide the exact code to be implemented but describes the processes & principles that need to be followed in order to implement these analyses.

There are five steps in simple MI process.

1. Check missing data patterns;
2. Impute non-monotonic / intermittent data – leaving only monotone missing data;
3. Use monotone regression to impute monotone missing data & create multiply imputed data sets;
4. Run the efficacy analyses (PROC GENMOD, PROC MIXED) on the multiply imputed data sets;

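### SAP 8.6.3 yields 15 p-values for ItchyQoL, its subscales and PROMIS; 13 lie outside the fixed sequence, and no sentence stops p<0.05 there being called statistically significant

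*SAP*

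**What the plan says.** **What is tested.** SAP 8.5.1.2 says the mixed model will report "p-values (where applicable) for mean change at all visits between treatments (NAL ER vs. placebo". SAP 8.6.3 narrows this to PROMIS sleep and the quality-of-life scale, and for the latter orders: "p-values for mean change at all time points between treatments (NAL ER vs. placebo) for ItchyQoL (total score and subscales: symptoms, functional limitations, emotions". The SAP appendix gives the visits for these questionnaires: "ADQS will use 3 visits (AVISITN 3-5/Week 6, 10, 14". The paragraph in 8.6.3 also names the Week 14 difference as the comparison that matters.

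**What is gated.** The SAP section headed Multiplicity lists ItchyQoL and PROMIS at Week 14 only, seventh and eighth of nine items, with no subscale and no earlier visit. It adds: "As soon as one endpoint assessment is found to be non-significant, subsequent endpoints will not be assessed". Protocol 13.4.6.3 also has both at Week 14 only, in a different order, and lets an endpoint reach significance only if the one before it did. SAP Section 9, item 3 says instead that ItchyQoL and PROMIS were taken out of the ranking.

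**What counts as significant.** SAP 8.1 sets the default: "all statistical testing will be two-sided and will be performed using a significance (alpha) level of 0.05". Under the primary-endpoint heading, the decision rule reads: "Unless otherwise indicated, all tests will be 2-sided, and differences resulting in a p-value <0.05 will be considered statistically significant".

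**What is labelled.** Subgroup results carry a caveat: "These subgroup analyses will be considered exploratory, as they do not control for multiplicity". The extra ItchyQoL and PROMIS p-values carry none.

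**The concern.** The SAP promises Type I error control for a defined set of endpoints, then orders further p-values on quality-of-life domains and earlier visits under a rule whose wording reaches every test. The subscales are not listed endpoints in either document, and the ItchyQoL objective names the total score. A report that followed the SAP literally could state a statistically significant effect on, say, the emotions subscale, or on sleep at Week 6. No part of the error-control plan would support that statement, and it could be made even if the primary comparison had failed.

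**Working it through.** The documents give no error rate and no test count for these p-values, so the plan has no figure of its own to reproduce here.

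**Step 1: count the tests.**
- Measures (SAP 8.6.3): ItchyQoL total, symptoms, functional limitations, emotions, PROMIS = 5.
- Post-baseline double-blind visits (SAP appendix): Weeks 6, 10, 14 = 3.
- Total: 5 × 3 = 15.

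**Step 2: subtract those in the sequence.**
- Under the SAP Multiplicity list, or under protocol 13.4.6.3: ItchyQoL total and PROMIS at Week 14, so 15 − 2 = 13 outside.
- The 13 are 5 × 2 = 10 tests at Weeks 6 and 10, plus 3 subscale tests at Week 14.
- Under SAP Section 9, item 3: 15 − 0 = 15 outside.

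**Step 3: expected false positives.** With no true effect, 13 × 0.05 = 0.65, whatever the correlation.

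**Step 4: chance of at least one p<0.05 among the 13, with no true effect.** This depends on correlations that the documents do not give, so they are assumptions:
- r_m is the correlation between measures (three subscales and PROMIS), and r_v the correlation between visits. Both are varied from 0.5 to 0.8.
- The correlation between different measures at different visits is r_m × r_v.
- ItchyQoL total is built from the subscales with weights 6:7:9, the item counts in SAP 7.3.2.
- Simulated multivariate normal statistics (400,000 draws), counting |z| > 1.96. The favourable column counts z > 1.96 in NAL ER's direction only.

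| r_m | r_v | any of 13, two-sided | any of 13, favouring NAL ER |
|---|---|---|---|
| 0.5 | 0.5 | 0.343 | 0.174 |
| 0.5 | 0.8 | 0.277 | 0.139 |
| 0.8 | 0.5 | 0.258 | 0.129 |
| 0.8 | 0.8 | 0.205 | 0.103 |

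The two-sided range is about 0.20 to 0.34. For the favourable direction I quote 0.10 to 0.18, slightly wider than the table, to allow for other ways of building the total.

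**Step 5: the three Week 14 subscales alone.** The chance is 0.126 at r_m = 0.5, 0.109 at 0.7 and 0.098 at 0.8, so about twice 0.05.

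**Step 6: sensitivity.** If all 13 tests share one common correlation, the chance is 0.33 at 0.5 and 0.14 at 0.9. If all 15 are outside the sequence, the structured model of Step 4 gives 0.213 to 0.362.

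**The case against.** The strongest reply is that the plan already sets priorities. SAP 8.6.3 names Week 14 as the comparison that matters, and the listed endpoints are at Week 14. The decision rule is printed under the primary-endpoint heading, and producing a p-value is not declaring significance. Part of this stands. Ten of the 13 tests are at Weeks 6 and 10, and the Week 14 sentence ranks them lower. It does not call them nominal or exploratory, however, and it does not touch the three Week 14 subscale tests. The position of the decision rule makes its reach arguable, but its wording covers all tests, and SAP 8.1 separately sets 0.05 for all testing.

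A reader might infer more than the documents support:

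- **That the fixed sequence is inflated.** It is not. The 13 tests do not feed into it, and its 0.05 was promised only for the endpoints in it.
- **That ItchyQoL or PROMIS at Week 14 could still be declared significant after the sequence stops.** The SAP stop rule and protocol 13.4.6.3 both bar this, and the decision rule yields where something else is indicated. What the SAP lacks is a description for a p-value that is printed anyway.
- **That the error could reach ten times 0.05.** That needs 13 independent tests: 1 − 0.95^13 = 0.487. Independence is impossible, because the ItchyQoL total is the sum of its subscales.
- **That WI-NRS mean change and IGA-PN activity show how to handle this, since 8.6.3 reports them without p-values.** Both are ranked in the SAP sequence (third and second), where a test is needed. Their missing p-values are a separate inconsistency, not a safeguard.

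**Conclusion.** The concern holds in a limited form. Thirteen p-values (15 if Section 9, item 3 governs) fall outside the fixed sequence with no exploratory label, and a rule worded for all tests lets any of them be called statistically significant. The consequence is the risk of unsupported secondary claims; the primary inference and the sequence's own error rate are unaffected. Across the assumed 0.5 to 0.8 correlations, the chance of at least one false result among the 13 is roughly four to seven times 0.05 (0.20/0.05 = 4; 0.34/0.05 = 6.8). The test count rests on the documents; the probability rests on the assumed correlations and on no true effect in any of the 13. This should be corrected, because the plan's own wording, and not only a missing label, permits the claim.

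**What to change.** 1. In the SAP decision rule under the primary-endpoint heading, state that p<0.05 is declared statistically significant only for the primary endpoint and for endpoints reached in the fixed sequence. This agrees with protocol 13.4.6.3.
2. In SAP 8.6.3, label as nominal and exploratory, with no significance claim: the ItchyQoL subscale p-values at all visits, the Week 6 and Week 10 p-values, and the p-value of any ranked endpoint that comes after the sequence has stopped. Repeat the label as a table footnote.
3. Reconcile the SAP Multiplicity list with Section 9, item 3 on whether ItchyQoL and PROMIS are ranked.
4. Do not use WI-NRS mean change or IGA-PN activity as models for reporting intervals only; resolve their missing p-values separately.

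The labelling costs a few sentences and a footnote. It needs no new data and leaves the sample size and the primary analysis unchanged. The downside is that subscale and early-visit results can no longer be called statistically significant.

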7.3.4. Prurigo Activity Score (PAS)

The PAS consists of 5 quantitative and qualitative measurements related to the examination of the skin: Type; number; distribution; quantitative number of lesions in a representative body part; and activity. Prurigo lesion activity is recorded as a stage (0 to 4), based on the percentage of overall lesions with the relevant characteristic.

Three types of PAS responders are defined, one for each of the following items: Prurigenous lesions with excoriations/crusts (item 5a); Healed lesions (item 5b); Number of lesions (item 2). For each of these, a responder is defined as a subject who has at least 1-category improvement in the relevant item from baseline to Week 14. For all three, a patient who does not have Week 14 measurement is a non-responder.

7.3.5. Investigator Global Assessment – Prurigo Nodularis (IGA-PN).

The IGA-PN collects an Investigator Global Assessment of the status of the PN skin lesions. The IGA-PN uses a 5-category scale (scoring 0 to 4) for assessing the status of 2 aspects of the disease: The Activity (amount of excoriation and crusting associated with the prurigo lesions), and the Stage (the quantitative presence and proportion of flattening of the lesions). An IGA-PN responder for Activity or Stage is defined as a subject who has at least 1-category improvement in the respective score from baseline to Week 14.

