8.6.1.3. Sensitivity Analysis for Subjects who take Prohibited Medications

This analysis is to assess the impact of concomitant medications that might affect the primary endpoint. The medications listed below are considered inter-current events (ICEs) confounding with the efficacy outcomes.

- μ -opioid receptor agonists (e.g., codeine, oxycodone, hydromorphone, oxymorphone, morphine, fentanyl, tramadol, butorphanol, pentazocine, meperidine, methadone)
- Opioid receptor antagonists naltrexone and nalmefene
- Antihistamines (topical or systemic)
- Topical calcineurin inhibitors
- Topical corticosteroids
- Topical capsaicin
- Anti-convulsant class drugs
- Cannabinoid agonists
- Topical doxepin
- Thalidomide or methotrexate
- Cyclosporin A
- Biologics with an immune suppressive effect*
- Investigational drug products*
- Cryosurgery
- UV-therapy

Efficacy data on subjects who experience an ICE will be set to missing at the designated time points after the start of such events. The analysis will provide an answer to the question that is crucial to individual subjects; “If I take this study medication as part of my treatment regimen, without adding any further medications that may impact the underlying disease, what response (response is defined as a ≥ 4 -point reduction in the 7-day average WI-NRS) might be anticipated after 14 weeks?”

Sensitivity analysis using missing data handling approaches will also be performed as outlined in the [Appendix](#).

In addition, the primary endpoint will be analyzed using the PP population.

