- Change in PAS as assessed by the percentage of subjects having a 1-category improvement in the percentage of healed lesions (item 5b) from baseline to Week 14 for the NAL ER treatment arm versus the placebo arm;
- Change in PAS as assessed by the percentage of subjects having a 1-category improvement in the percentage number of lesions (item 2) from baseline to Week 14 for the NAL ER treatment arm versus the placebo arm;
- Change in IGA-PN as assessed by the percentage of subjects having a 1-category improvement in activity from baseline to Week 14 for the NAL ER treatment arm versus the placebo arm;
- Change in IGA-PN as assessed by the percentage of subjects having a 1-category improvement in stage from baseline to Week 14 for the NAL ER treatment arm versus the placebo arm;
- The proportion of subjects with PBI-P ≥ 1 at Week 14 for the NAL ER treatment arm versus the placebo arm;
- The proportion of subjects with PBI-P ≥ 2 at Week 14 for the NAL ER treatment arm versus the placebo arm;
- The proportion of subjects with PBI-P ≥ 3 at Week 14 for the NAL ER treatment arm versus the placebo arm.

In addition, shift tables from baseline for improved ≥ 1 , no change, worsened ≥ 1 , and discontinued at Week 14 will be presented for PAS (item 5a), PAS (item 5b), PAS (item 2), IGA-PN for Activity, and IGA-PN for Stage.

Logistic Regression for Categorical Endpoints

The logistic regression model used for the primary endpoint will also be used for several secondary efficacy endpoints. Subjects with missing Week 14 measurement are treated as non-responders. Response rate, standard error, OR between the treatment groups, 95% confidence interval and p-values will be provided. The endpoints are:

- Change in PAS as assessed by the percentage of subjects having a 1-category improvement in the percentage of pruriginous lesions with excoriations/crusts (item 5a) from baseline to Week 14 for the NAL ER treatment arm versus the placebo arm;
- Change in IGA-PN as assessed by the percentage of subjects having a 1-category improvement in activity from baseline to Week 14 for the NAL ER treatment arm versus the placebo arm (95% CI only, with no p-value).

Sensitivity analysis for PAS (item 5a)

The sensitivity analysis to assess the impact of concomitant medications use for the primary endpoint will also be used for PAS (item 5a).

For open-label period visits, descriptive statistics will be displayed by treatment and overall for all secondary variables.

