9 CHANGES TO PLANNED ANALYSIS FROM STUDY PROTOCOL

The following changes were agreed upon

1. Sites were changed from random effects to region (US or Europe) which is being treated as a fixed effect.
2. LOCF was excluded from imputation methods.
3. The ranked outcome for adjustment for multiplicity was changed. The ItchyQoL measure & the PROMIS scale were excluded from the ranking and replaced with PAS (5a)
4. The analyses for prohibited medication were changed to set all efficacy outcomes to missing from the date of ingestion of the prohibited medication. Previously, missing outcomes were set = non-responders.
5. A new set of simple multiple imputation models were added to assess the impact of missing efficacy measures due to the use of prohibited medications.

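### In the prohibited-medication sensitivity analysis of PAS item 5a, values set to missing run into the PAS non-responder rule, so on a literal reading medication users become failures

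*SAP*

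**What the plan says.** SAP 8.6.1.3 treats a list of medications as intercurrent events. Its rule is: "Efficacy data on subjects who experience an ICE will be set to missing at the designated time points after the start of such events". The stated aim is to tell a patient what response to expect from study drug when no other medication that could affect the disease is added.

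SAP 8.6.3, under its heading for the PAS 5a sensitivity analysis, extends this: "The sensitivity analysis to assess the impact of concomitant medications use for the primary endpoint will also be used for PAS (item 5a".

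Two places govern a missing PAS value. SAP 7.3.4, which defines responders for items 5a, 5b and 2, says: "For all three, a patient who does not have Week 14 measurement is a non-responder". The logistic regression paragraph of 8.6.3, which lists PAS 5a, says: "Subjects with missing Week 14 measurement are treated as non-responders".

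SAP section 9 records two relevant changes. Item 4 says the prohibited-medication analyses now "set all efficacy outcomes to missing from the date of ingestion of the prohibited medication", and adds: "Previously, missing outcomes were set = non-responders". Item 5 says: "A new set of simple multiple imputation models were added to assess the impact of missing efficacy measures due to the use of prohibited medications".

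For the primary endpoint, SAP 8.6 (Analysis of Primary Efficacy Endpoint) says: "Missing Week 14 WI-NRS data will be set to missing".

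**The concern.** The analysis removes data in order to ask a hypothetical question, and the PAS derivation then turns a removed value into a definite failure. For WI-NRS the removed value stays missing or is imputed. One named analysis would therefore estimate different quantities for the two endpoints.

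PAS 5a is a key secondary endpoint, and this is the only analysis the SAP names for it that addresses concomitant medication. If users are scored as failures, the result depends on how many subjects in each arm took a listed product. It then no longer shows whether the lesion finding survives once the influence of those products is taken out.

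The number affected need not be small. The 8.6.1.3 list includes topical corticosteroids, topical capsaicin, topical doxepin, and antihistamines whether topical or systemic. Protocol 10.6.4 allows one limited topical itch intervention during the first 10 weeks, and exclusion criterion 22 allows systemic antihistamines at a stable dose.

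**Working it through.** The SAP gives no figure to reproduce here. The check is a trace through the rules, then an illustration.

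**Trace.** Take a subject who uses a listed topical product in the first 10 weeks, attends Week 14, and has improved by at least one category on item 5a.

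1. Main PAS 5a logistic regression: nothing is removed for medication use, so the subject is a responder.
2. Sensitivity analysis, 8.6.1.3 applied through 8.6.3: the Week 14 PAS 5a value is set to missing.
3. SAP 7.3.4 and the 8.6.3 logistic paragraph: missing at Week 14, so the subject is a non-responder.
4. Section 9 item 4: non-responder scoring is described as the superseded rule.
5. The same subject's WI-NRS: missing after the event and left missing, or imputed. No non-responder rule intervenes.

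No text exempts PAS values removed in step 2 from step 3.

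**Does the imputation appendix settle it?** SAP 8.6.1.3 ends by pointing to the Appendix, and section 12.3 names PAS 5a among the secondary endpoints. However, its method is monotone regression on continuous scores. The visits are Weeks 2, 6, 10 and 14 for one dataset and Weeks 6, 10 and 14 for the other. PAS 5a is a five-category item and is scheduled after baseline only at Weeks 10 and 14 of the double-blind period (SAP Table 1; there is no Week 6 PAS window in 7.2.7). The appendix neither ranks the two rules nor gives a model that fits PAS 5a.

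**Illustration.** All inputs are assumed, because the documents give neither Week 14 PAS 5a response rates by arm nor rates of listed-medication use. Let p be the response rate and u the share of the arm using a listed product (T = NAL ER, C = placebo), with users responding like non-users.

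- Left missing: pT − pC
- Scored as failure: pT(1 − uT) − pC(1 − uC)

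| pC / pT | uC / uT | Left missing | Scored as failure |
|---|---|---|---|
| 35% / 35% | 20% / 10% | 0 | 31.5 − 28.0 = +3.5 points |
| 30% / 45% | 20% / 10% | 15.0 | 40.5 − 24.0 = 16.5 points |
| 30% / 45% | 10% / 10% | 15.0 | 40.5 − 27.0 = 13.5 points |
| 30% / 45% | 10% / 20% | 15.0 | 36.0 − 27.0 = 9.0 points |

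**Relaxing the assumption.** Suppose users, had they not taken the product, would respond at rate q. The target in an arm is (1 − u)p + uq. Failure scoring gives (1 − u)p, which is too low by uq. The error in the difference is uC·qC − uT·qT. For the use rates in the first row:

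- q = 35%: 7.0 − 3.5 = 3.5 points
- q = 17.5% (half): 3.5 − 1.75 = 1.75 points
- q = 0: 0 points

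Simply dropping users gives p, which is too high by u(p − q). Neither shortcut is right in general.

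**The case against.** The strongest reply is that a rule written for one named analysis overrides a general derivation. 8.6.3 imports the primary endpoint's sensitivity analysis as a whole, including its pointer to imputation, and section 9 items 4 and 5 show the same intent. On this view 7.3.4 concerns subjects never assessed at Week 14, whereas a medication user who attended does have a measurement that the analyst later masks. This is a plausible account of what was meant, but the SAP does not say it. The 8.6.3 logistic paragraph speaks of missing measurements, which is also what 8.6.1.3 makes of these values.

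A second reply is that counting medication use as failure is a recognised composite strategy. That is true, but it answers a different question from the one 8.6.1.3 poses, and section 9 says it was given up.

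A third is that missing WI-NRS and missing PAS are already handled differently in the main analyses. That is also true. It does not explain why an analysis with a single stated aim should inherit the difference.

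Two points on this side stand in full. The size is hypothetical, and it shrinks if users would have responded less often than non-users, which is plausible where use follows debilitating itch. And the primary endpoint's imputation cannot simply be copied to PAS 5a.

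**Conclusion.** The point holds as a conflict between stated rules, confined to one sensitivity analysis. Read literally, the SAP scores listed-medication users as PAS 5a failures in an analysis meant to estimate response without added medication.

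A reader might infer that the key secondary result itself shifts. The documents do not support that: the main PAS 5a logistic regression removes nothing for medication use, so its estimate, p-value and place in the fixed testing sequence are the same under either reading. Nor can one infer a bias towards NAL ER. In the illustration the difference rises when placebo subjects use more and falls when NAL ER subjects use more or use is equal.

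The illustrative +3.5 points rests on assumed response and use rates and on users responding like non-users. It shows that the two readings can disagree, not by how much they will.

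**What to change.** State in SAP 7.3.4 and 8.6.3 that:

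- The non-responder rule does not apply to PAS 5a values set to missing under 8.6.1.3.
- In that sensitivity analysis those values are multiply imputed with a binary or ordinal model using treatment, baseline PAS 5a, and any Week 10 PAS 5a recorded before the event.
- Subjects with no Week 14 PAS for any other reason, and with no prior listed-medication use, remain non-responders. A subject who uses a listed product and then drops out before Week 14 therefore falls under the imputation.

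The cost is a precedence sentence, a short PAS-specific imputation specification in section 12.3, and a flag in the analysis dataset marking values removed under 8.6.1.3. No new data are needed and the main analysis does not change.
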